12.2.1 Severity

The study physician will use the following guidelines to determine level of severity:

Mild: Awareness of signs or symptoms, but easily tolerated and causing no loss of time from normal activities. No specific medical intervention is required.

Moderate: Discomfort enough to cause a low level of inconvenience or concern to the participant and may interfere with daily activities. Symptoms may require minimal, local, or noninvasive medical intervention only.

Severe: Events interrupt the participant's normal daily activities and are usually incapacitating. Significant symptoms may require hospitalization or invasive medical intervention.

Life threatening: Events that may involve acute, life-threatening metabolic or cardiovascular complications (such as circulatory failure, hemorrhage, sepsis) or life-threatening physiological consequences. Intensive care or emergent invasive procedure is required.

Fatal: Causing death.

Severity is not synonymous with seriousness. A severe headache is not necessarily an RAE. However, mild chest pain may result in a day's hospitalization and thus would be classified as an RAE.

12.2.2 Expectedness

An independent safety monitor (ISM) will assess AEs as to whether they were expected or unexpected based on current knowledge. Categories are:

Expected: An AE that is anticipated on the basis of prior experience with the intervention under investigation; an event that can be attributed to the underlying condition of the participant being

studied; or an event that can be attributed to the patient population being studied (see section 12.3). Expected AEs are captured in a standardized way every four weeks.

Unexpected: An AE that was not anticipated on the basis of prior experience with the intervention under investigation; an event that cannot be attributed to the underlying condition of the participant being studied or to the patient population; or an expected event whose frequency or severity exceeds what was anticipated (see section 12.4.2). Unexpected AEs are reportable.

12.2.3 Relatedness

The ISM will determine the degree to which RAEs are related to study procedures.

Definitely related: The adverse event is clearly related to the investigational procedure – i.e., an event that follows a reasonable temporal sequence from administration of the study intervention, follows a known or expected pattern of response to the study intervention, that is confirmed by improvement on stopping and reappearance of the event on repeated exposure, and that could not be reasonably explained by the known characteristics of the participant's clinical state.

Possibly related: An adverse event that follows a reasonable temporal sequence from administration of the study intervention or that follows a known or expected pattern of response to the study intervention, but that could readily have been produced by a number of other factors.

Not related: The adverse event is clearly not related to the investigational procedure (i.e., another cause of the event is most plausible; and/or a clinically plausible temporal sequence is inconsistent with the onset of the event and the study intervention and/or a causal relationship is considered biologically implausible).

12.3 Expected AEs

Expected AEs will be captured through telephone interviews every four using the Expected Adverse Events Form. Following are expected adverse events that have been listed in the ICF:

- foot pain
- hip pain
- back pain
- knee pain
- digestive or stomach pain
- breathing problems
- chest pain or discomfort
- bloating or puffiness in the legs, ankles, or feet
- drowsiness, dizziness, or confusion
- shakiness, anxiety, clammy skin, or irritability
- fall (with or without injury)

12.4 Reportable AEs

RAEs are events that have potential implications for participant safety and that require individual reporting. RAEs will be defined as events that fall into at least one of the following categories:

1. Serious adverse events (SAEs)
2. Unexpected AEs, and
3. Injury that occurs while a participant is under the supervision of study personnel.

Events that cannot be clearly defined as “reportable” will be discussed with the study physician and PI to determine if they should be reported.

12.4.1 Serious Adverse Event (SAE)

SAEs will be defined as any event that:

- Results in death
- Is life threatening, or places the participant at immediate risk of death (e.g., MI, stroke/TIA)
- Requires or prolongs hospitalization
- Causes significant disability or incapacity (e.g., torn muscle or ligament)
- Requires medical or surgical intervention to prevent significant disability (e.g., hip fracture)

SAEs will be assessed through telephone interviews every four weeks using the Reportable Adverse Events Telephone Screening Form. SAEs will also be assessed at the beginning of each PT visit and clinical site visit, and by any study staff who learns of a serious event.

12.4.2 Unexpected Adverse Event

Unexpected AEs will be defined as medical events that occur during study participation, but do not commonly occur in the study population and which are not listed in the ICF or study protocol (section 12.3). An unexpected AE may be witnessed by a member of the research team, or staff may be told about an unexpected event that may meet the criteria for reporting.

Unexpected AEs that have a potential relationship to study procedures and activities will be captured on an Incident Report and submitted to the study office where they will be logged in the participant binder and then reported to the Independent Safety Monitor (ISM).

A reportable unexpected AE will be one that meets all of the following criteria:

- Unexpected, in terms of nature, severity, or frequency, given (a) the research procedures that are described in the protocol-related documents, such as the IRB-approved research protocol and ICF; and (b) the characteristics of the study population;
- Related or possibly related to participation in the research (meaning that there is a reasonable possibility that the incident, experience, or outcome may have been caused by the procedures involved in the research);
- Suggests that the research places participants or others at a greater risk of harm (including physical, psychological, economic, or social harm) than was previously known or recognized.

The medical and scientific judgment of the study physician and the PI will be exercised in deciding whether an occurrence should be reported. In addition, difficulty determining whether or not an event is unexpected and/or attributable to the intervention will be addressed by the ISM, who will determine if the event is to be reported.

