12.2 Classifying Adverse Events

An AE is any unfavorable or unintended medical occurrence in a human study participant that has taken place during the course of a research project, including any abnormal sign, symptom, or disease, whether or not related to participation in the research

For the purposes of this study, any event that meets the criteria for an SAE, is unexpected, or results in injury to the participant while s/he is under the supervision of study related personnel will be classified as an RAE.

Adequate review, assessment, and monitoring of RAEs require that they be classified as to severity, expectedness, and potential relatedness to the study intervention.

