12.6 Evaluation and Follow-up of RAEs

All RAEs will be forwarded to an ISM for adjudication and follow-up. The ISM may contact the study coordinator to request additional information from the participant, significant other, or their health care provider and may seek medical records from a physician or care setting if needed to make a determination about relatedness to the study. If the event is potentially related to the study, the ISM will consider whether the event was listed in the protocol and ICF and whether modifications to the protocol and ICF should be considered. To ensure the appropriate classification of events, the study physician and/or PI may also be called on to provide additional information.

The ISM will be responsible for providing follow-up for ongoing reportable events, as follows:

1. The ISM will make a determination about relatedness and expectedness of the event and submit a Reportable Adverse Event Evaluation to the study coordinator.
2. If there are follow-ups to an event (and the event is ongoing), the ISM will complete the RAE Follow-up Form to record any updates and submit to the study coordinator.
3. The ISM will follow up on RAEs until a final status has been determined for the event (e.g., recovered, ended in death, is still present, or status is unknown). Some RAEs may have a status of still present at the conclusion of the study. These are the categories of RAE status:
 - a. 'Resolved' is an event that has ended, with or without residual deficits.
 - b. 'Still present' is an event that is ongoing.
 - c. 'Unknown' should be used when the site is unable to make contact with the participant or proxy or to obtain additional information in any other way.
 - d. 'Died' is for an event that ended in death.
4. Once the event is no longer ongoing and a final status for the event has been determined by the study physician, the ISM will confirm the final status, record the closed date, and sign and date the RAE Final Status Form that will be submitted to the study coordinator.

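### Section 12.4.2 makes an unexpected adverse event reportable only under conditions that five other sections do not impose, so some events change status and one group may never reach the independent safety monitor

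*Protocol*

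**What the plan says.** **The unconditional rule.** Protocol section 12.2 classifies as an RAE "any event that meets the criteria for an SAE, is unexpected, or results in injury to the participant" under study supervision. The alternatives are joined by *or*, so being unexpected is enough. Section 12.2.2 says the same without qualification: "Unexpected AEs are reportable". Section 12.4 says "RAEs will be defined as events that fall into at least one of the following categories", and its second category is unexpected AEs with nothing added. Sections 9.6.3 and 12.1 also list unexpected AEs among the RAEs.

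**Who then reviews.** Section 12.6: "All RAEs will be forwarded to an ISM for adjudication and follow-up". Section 12.2.3: "The ISM will determine the degree to which RAEs are related to study procedures", with a category for events that are not related. Section 12.7.2 repeats that relatedness and expectedness are for the ISM.

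**The conditional rule.** Section 12.4.2: "A reportable unexpected AE will be one that meets all of the following criteria". The event must be unexpected in nature, severity or frequency; it must be "Related or possibly related to participation in the research"; and it must be one that "Suggests that the research places participants or others at a greater risk of harm" than was known before. The study physician and the PI exercise the judgment on whether to report. The same section sends unexpected AEs with a potential relationship to study procedures to the ISM by Incident Report, and refers to the ISM cases where expectedness or attribution is hard to settle.

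**The concern.** The two rules cannot both define a reportable unexpected AE, and the difference affects who sees the event. Elsewhere the protocol has the ISM decide relatedness on events already received. Item 3 of the reporting timeline in 12.5 concerns events that the ISM has reviewed and then classified as related or possibly related. Section 12.6 describes what the ISM does if an event is potentially related, which presupposes that some events received are not. Section 12.4.2 puts a relatedness screen by the study team before that review.

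Safety and tolerability is a stated objective (section 4.2). Everyone in the pilot receives PUSH Plus Protein, so no concurrent group within it could reveal an excess of some unlisted symptom. A non-serious event that nobody anticipated, and that the team readily puts down to something else, is a case where a second, independent opinion is useful. The RAE table sent to the DSMB under 12.8 would also mean different things depending on the section applied.

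**Working it through.** No sample size, power figure or event count enters this point, so the check is a comparison of text. Take an AE that is unexpected, not serious, and not an injury under study supervision. The broad rule is that of sections 9.6.3, 12.1, 12.2, 12.2.2 and 12.4, followed by forwarding under 12.6.

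| Team's view of the event | Broad rule | Section 12.4.2 | Reaches ISM under 12.4.2? |
|---|---|---|---|
| (a) Confidently unrelated | RAE, forwarded | Not reportable (fails relatedness) | No: the Incident Report needs a potential relationship, and no difficulty is raised |
| (b) Possibly related, not risk-raising | RAE, forwarded | Not reportable (fails greater risk) | Yes, by Incident Report |
| (c) Possibly related and risk-raising | RAE, forwarded | Reportable | Yes |
| (d) Team finds expectedness or attribution hard to judge | RAE if unexpected | ISM decides | Yes |

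Reading across:

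1. RAE status differs in rows (a) and (b). The RAE count therefore depends on the section followed.
2. Loss before ISM review occurs only in row (a), and comes from the relatedness screen alone.
3. Serious AEs and supervised injuries are outside the table. Sections 12.4, 12.4.1 and 12.4.3 make them reportable in their own right, whatever their relatedness.
4. The ISM's power in 12.7.2 to confirm or refute RAE classification does not recover row (a), because it applies to events the ISM has been sent.

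Two further mismatches appear in the same comparison. First, 12.2.2 counts as unexpected an expected event whose frequency or severity exceeds what was anticipated. The opening definition in 12.4.2 covers only events that are uncommon in the population and not listed in the consent form or protocol, although its own first criterion then mentions severity and frequency. Second, 12.4 takes events of unclear reportability to the study physician and PI, whereas 12.4.2 takes difficult ones to the ISM.

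**The case against.** The strongest reply is that 12.4 is the general statement and 12.4.1 to 12.4.3 define its three categories, so 12.4.2 simply says what the second category means. Section 12.4 also opens by describing RAEs as events with potential implications for safety, and it already allows triage by the study physician and PI. This reading is possible, but it does not dispose of the conflict. Sections 12.2 and 12.2.2 stand outside 12.4 and carry no condition, and 12.1 lists events with safety implications alongside unexpected AEs rather than as a limit on them. The reading also leaves the relatedness screen ahead of the person assigned to judge relatedness.

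Other parts of the reply do stand, and they rule out three stronger conclusions that a reader might draw:

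- *That the full three-part test controls access to the ISM.* It does not. The Incident Report route takes every unexpected AE with a potential relationship to the ISM, risk-raising or not, and difficult cases go there too. Nor has relatedness been handed over wholesale to the study team.
- *That everything outside the 11 expected items in 12.3 is affected.* Under 12.2.2, expected also covers events attributable to the participant's underlying condition or to the patient population, so the affected pool is smaller.
- *That the DSMB sees nothing of such events.* Section 12.8 provides semi-annual tabulations of non-serious and expected AEs. How a row (a) event would enter them is not stated: the standard form covers the listed expected items, and 12.4.2 names no form for an unexpected event thought unrelated. The text does not show that the event is excluded, only that no route is given.

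Figures 5b to 5d are not visible in the text reviewed. They may show routing detail, but could not make the two written definitions agree.

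**Conclusion.** The inconsistency is real and narrow. Five sections make being unexpected sufficient for RAE status; 12.4.2 adds two further conditions. Among events that are neither serious nor supervised injuries, following 12.4.2 means that (a) unexpected AEs confidently judged unrelated are not reportable and do not reach the ISM, and (b) possibly related AEs not thought risk-raising reach the ISM but are not reportable. Both groups are RAEs under the broad rule.

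The number of events cannot be derived from the documents, which give no expected rate of non-serious unexpected AEs. The conclusion assumes that staff apply 12.4.2 as written and that the unseen figures do not add a route for group (a). It does not touch the primary walking-distance comparison. It concerns the completeness of independent safety review and the meaning of the pilot's RAE count, and is worth correcting because the correction is cheap.

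**What to change.** 1. Use one definition of a reportable unexpected AE throughout, that of 12.2, 12.2.2 and 12.4.
2. Record every unexpected AE and forward it to the ISM, so that relatedness is judged after receipt, as item 3 of the timeline in 12.5 already assumes. Bring the sentence in 12.4 on unclear events into line with this.
3. Remove the three-part test in 12.4.2 as a condition for RAE status or for ISM review.
4. If the test is kept for some later reporting step, say that it neither replaces nor narrows the existing triggers. Under 12.5 item 3, a related or possibly related classification by the ISM is enough for submission to the OAIC Program Director, with no greater-risk condition. Section 12.8 separately requires immediate reporting of RAEs that relate to intervention hazards or cause urgent concern. Making the three-part test the general trigger for expedited reporting would raise the bar in 12.5 and could conflict with 12.8.
5. Reconcile the two definitions of unexpected in 12.2.2 and at the opening of 12.4.2.
6. Check Figures 5b to 5d against the reconciled text.

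The cost is a wording amendment and a few more events for the ISM to review in a study of 30 participants.

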12.4.3 Injury that Occurs while Under the Supervision of Study Related Personnel

Any injury that occurs while the participant is under the supervision of study-related personnel is reportable. The injury can happen on site (during an assessment visit) or off-site (in the participant’s home during a PT visit or if the study offers supervision during transportation). These events will be captured on the Reportable Adverse Events Form.

12.5 Expected AE and RAE Collection and Reporting

The requirements for reporting RAEs will begin when the participant provides informed consent and will end 30 days after the participant's involvement in the study has ended. Expected AEs will be assessed every four weeks after baseline testing. Figures 5a-d provide algorithms describing the reporting process.

Figure 5a. Collection and Reporting Process for Expected AEs

[figure not shown]

Figure 5b. Collection and Reporting Process for RAEs Collected during Standardized Telephone Interviews

[figure not shown]

Figure 5c. Collection and Reporting Process for RAEs Identified Anytime Other than During a Standardized Telephone Interview

[figure not shown]
[figure not shown]

Figure 5d. Review and Reporting Process for RAEs

Timeline for Reporting Events

The RAE reporting schedule is shown below:

1. Staff will report RAEs to the PI and study physician as soon as the event is known and submit documentation of the event to the study coordinator in real time.
2. All injuries that occur while a participant is under the supervision of study personnel and all participant deaths (regardless of relatedness) will be reported to the OAIC Program Director within 24 business hours (excluding weekends and holidays) of the PI becoming aware of the event.
3. Events that are reviewed by the ISM and subsequently classified as related or possibly related to the research will also be submitted to the OAIC Program Director.
4. All other RAEs, SAEs, expected AEs, and protocol deviations will be requested semiannually by the OAIC to be presented to the DSMB.

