8.6 Scheduling Intervention Visits

There are three requirements for scheduling of intervention visits:

1. The first intervention visit should occur on Day 7 or earlier, where the last day of baseline testing = Day 0.
2. The schedule of intervention visits is anchored to the date on which baseline testing is completed regardless of when the intervention starts.
3. Intervention visits should never occur on two consecutive days, even when moving from one week to the next.

Participants who provide required baseline data are eligible to receive the intervention; however, the intervention will not begin until after the date all baseline measures are completed. Baseline data collection must be completed within 14 days of the SMWT. Week 1 will begin on the day of the first intervention visit or on Day 7 after baseline testing is complete, whichever is earlier.

Subsequent weeks will start on the same day of the week as Week 1. For example, if the participant's first intervention visit is on a Wednesday, each intervention week for that participant will extend from Wednesday to Tuesday (inclusively). Alternatively, if the first visit has not yet occurred by Day 7 and Day 7 is a Monday, then the participant's intervention weeks will extend from Monday to Sunday (inclusively).

In certain circumstances (e.g., illness, travel), the first intervention visit may be scheduled after Day 7.

Ideally participants will receive 2 visits per week for 16 weeks after complete baseline testing (32 visits total). However, missed visits in a given week can be replaced by makeup visits in subsequent weeks (not to exceed 3 visits in any given week) as long as the visits are on non-consecutive days. If the participant has not had 32 visits by the end of 16 weeks, makeup visits can be performed during the subsequent two weeks to get as close as possible to the target of 32 visits.

Section 9: Study Measures

A list of study measures is provided below. All of the measures will be interview-based or based on observations of performance or physiological assessments. No proxy data will be allowed at baseline. However, at the 16-week follow-up visit, a proxy may be contacted to provide information about the participant's walking ability. Also, the four-week phone calls to obtain information on recent health events will be conducted with a proxy when the participant is not available

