9.6.3 Reportable Adverse Events (RAEs)

Reportable adverse events (RAEs), which include serious adverse events (SAEs), unexpected AEs or injury that occurs under supervision by study staff, will also be obtained during the study. Participants will be screened for possible RAEs every four weeks during the telephone interviews using standardized questions. Participants (or their proxies) will be asked about life-threatening or significant medical events and the outcomes of these events. RAEs will also be asked about by study staff prior to each PT visit and clinical site follow-up assessment. RAEs may be spontaneously reported to any study staff member throughout the study (see section 12.4.1).

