10.2 Follow-up Assessment

The following measures will be obtained at 16 weeks after baseline testing.

- Reportable Adverse Events
- Six-Minute Walk Test
- Modified Mini-Mental State Examination
- Short Physical Performance Battery
- SF-36 Health Survey
- Weight and waist circumference
- Pepper Assessment Tool for Disability
- Mini Nutritional Assessment-Short Form
- Trail Making Test (Trails A and B)
- Blood draw (for serologic and genetic tests)
- CT scan of thigh
- DXA scans of hip and whole body
- GAITrite

- Four-Square Step Test
- Biodex strength testing (knee flexion/extension)

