10.3 Telephone Interviews

Structured telephone interviews will be conducted every four weeks for 16 weeks starting four weeks after the last date of baseline testing. The following measures will be administered:

- Reportable Adverse Events (RAE) Form
- Expected Adverse Events (AE) Form
- Self-reported adherence to protein and supplements

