10.4 Timing of Study Procedures

The target date for completion of the pre-baseline testing (i.e., screening) assessments will be anchored to the date of admission to the hospital for hip fracture. The target date for completion of all other assessments will be anchored to the date on which all baseline testing is completed (see Table 1).

Note: In cases where the participant performs all required baseline measures and then performs additional baseline measures, the date on which baseline testing is completed is defined as the date on which the participant performed the last assessment within the allowable window for baseline testing (up to 26 week post hospital admission). In cases where additional baseline measures have been scheduled but cannot be completed within the allowable window for baseline testing, (e.g., scheduling conflict, not safe), the date on which baseline testing completed is defined as the date on which staff establishes definitively that no additional baseline measures can or will be attempted.

Table 1. Timing of Study Procedures

PROCEDURE	TARGET DATE	ALLOWABLE INTERVAL
Phase 3 screening	As early as possible following admission	Up to 26 weeks post-admission
Baseline assessment	As early as possible following admission	Up to 26 weeks post-admission
Dietitian consult	1 week after baseline testing is completed	+1 week
First intervention visit	1 week after baseline testing is completed	+16 weeks
First telephone interview	4 weeks after baseline testing is completed	-1 week, +3 weeks
Subsequent telephone interviews	At 4-week intervals from date on which baseline testing is completed	-1 week, +3 weeks
First follow-up assessment	16 weeks after baseline testing is completed	+2 weeks
Out-of-window assessment	16 weeks after baseline testing is completed	0-16 weeks and 18-38 weeks after baseline testing is completed

At baseline, all participants will, by design, be tested at the clinical site. At the follow-up visit, we will attempt to test all participants at the clinical site. When this is not possible, we will attempt to have study staff administer the test in a non-study clinical facility or, failing that, at another non-study location or the participant's home.

Section 11: Safety Assessments

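### RAE reporting runs to 30 days after involvement ends, but no RAE question is scheduled in those days, so late SAEs reach the study only if someone volunteers them

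*Protocol*

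**What the plan says.** Protocol section 12.5 fixes both ends of the window: "The requirements for reporting RAEs will begin when the participant provides informed consent and will end 30 days after" involvement is over. The protocol does not define when involvement ends.

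Active questioning about RAEs is scheduled as follows:

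- **Baseline.** RAEs are on the list of baseline assessments (section 10.1).
- **Visits.** "RAEs will also be asked about by study staff prior to each PT visit and clinical site follow-up assessment" (section 9.6.3). Section 12.4.1 repeats this for SAEs.
- **Calls.** "Structured telephone interviews will be conducted every four weeks for 16 weeks starting four weeks after the last date of baseline testing" (section 10.3), which gives targets at weeks 4, 8, 12 and 16. Table 1 allows each call to be one week early or three weeks late.
- **Follow-up assessment.** "The following measures will be obtained at 16 weeks after baseline testing" (section 10.2), with RAEs first on the list. Table 1 allows two further weeks, and an out-of-window assessment at "0-16 weeks and 18-38 weeks after baseline testing is completed".
- **Make-up sessions.** If 32 PT visits have not been reached by week 16, "makeup visits can be performed during the subsequent two weeks" (section 8.6).

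Nothing later appears in sections 10.2 to 10.4. Other routes exist but are passive. Section 9.6.3 accepts spontaneous reports to any staff member, section 11.3 tells participants to report events whenever they occur, and section 12.4.1 covers staff who happen to learn of a serious event.

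**The concern.** The protocol asks for RAEs over a period in which nobody is scheduled to ask about them. During the intervention it does not rely on participants coming forward: it asks at each PT visit and every four weeks by telephone, and the introduction to section 9 allows a proxy to answer those calls. After the last contact this active system stops, while the reporting duty continues for 30 days.

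The events most likely to go unreported are deaths and incapacitating hospitalisations, because the participant is then least able to contact the study. Safety is a stated objective (section 4.2), and section 12.1 treats prompt and full capture of RAEs as essential to protecting participants. In a sample of 30, one participant whose serious event is missed changes the proportion with an event by 1/30 = 3.3 percentage points.

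**Working it through.** The documents give no figure for the share of the window without active questioning, so there is none to reproduce. The check is a count of days.

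**Inputs**

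- c = days from consent to completion of baseline testing. The protocol does not give this. Section 7.5 allows consent at any time after phase 1 screening and before 26 weeks post admission, so c is varied from 0 to 182 days. The top value is an outer bound, because baseline testing must also be finished by week 26.
- d = days from completion of baseline testing to the end of involvement: 16 × 7 = 112 on schedule, or 18 × 7 = 126 if the follow-up assessment uses its two-week allowance.
- u = days of the 30-day tail with no scheduled RAE question. If involvement ends at the last scheduled contact (an assumption, since the term is undefined), u = 30.

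**Formula:** share = u / (c + d + 30)

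**Last contact at week 16 (d = 112, u = 30)**

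- c = 0: 30/142 = 21.1%
- c = 28 (4 weeks): 30/170 = 17.6%
- c = 56 (8 weeks): 30/198 = 15.2%
- c = 84 (12 weeks): 30/226 = 13.3%
- c = 182 (26 weeks): 30/324 = 9.3%

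**Last contact at week 18 (d = 126, u = 30)**

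- c = 0: 30/156 = 19.2%
- c = 28: 30/184 = 16.3%
- c = 182: 30/338 = 8.9%

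**Involvement taken to end at week 16, last call made at week 19 (d = 112, u = 30 − 21 = 9)**

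- c = 0: 9/142 = 6.3%
- c = 182: 9/324 = 2.8%

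**Early end of involvement, for illustration at week 8 (d = 56, u = 30)**

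- c = 0: 30/86 = 34.9%

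The first and third sets show why the missing definition matters. With the same calendar, the uncovered tail is 30 days or 9 days depending on which contact marks the end. Late contacts help only if the 30 days are counted from an earlier date. If the late contact itself marks the end, the whole tail moves with it and stays uncovered.

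**What the tail can contain.** Falls, with or without injury, are on the list of expected AEs in section 12.3 and become RAEs only if they meet another criterion, such as seriousness. Injuries under study supervision can hardly arise once involvement has ended. Section 12.4.2 ties unexpected AEs to the period of study participation. That leaves mainly SAEs. The safety monitor's follow-up in section 12.6 tracks events already reported and does not find new ones.

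**The case against.** The strongest reply is that section 12.5 sets a duty to report, not a promise to ask. Its timeline has staff report an event once they know of it, and it uses different language for expected AEs, which are actively assessed every four weeks. A passive tail after active follow-up is a recognisable arrangement and does not contradict the schedule. This stands: a reader might infer that the protocol contradicts itself, and the text does not go that far.

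The second reply concerns harm. A reader might infer that the RAE rate is understated by up to 21%. The documents do not support that. Neither protocol section 14 nor the SAP plans an RAE rate per person-time. The event rates that section 12.8 asks the DSMB to watch concern non-serious and expected AEs, while RAEs go to it as individual records and tables. The 21% is also a maximum for someone who completes 16 weeks, because the window opens at consent and not at baseline.

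Third, participants are told to report events at any time, and section 12.5 refers to a pathway for RAEs found outside the interviews (Figure 5c). To say that the tail rests on chance would be too strong; it rests on unsolicited reports. The figures are not shown in the text available and the Manual of Procedures was not available, so a closing call described there cannot be excluded. It would, however, belong in sections 10.2 to 10.4, and none is listed.

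These replies limit the size and nature of the harm. They do not supply an active question in the last 30 days.

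**Conclusion.** The point holds as a gap in ascertainment that is cheap to close. RAE reporting extends 30 days past the end of involvement, and no scheduled contact covers that period. For a participant who completes 16 weeks, and whose involvement ends at the last scheduled contact, the uncovered part is about 9% to 21% of the window from consent to close; the upper figure requires consent to coincide with completion of baseline testing. It falls to 2.8% to 6.3% if involvement ends at week 16 and the last call is made at week 19, and exceeds 21% if involvement ends early enough.

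The consequence is that the SAE counts and tables sent to the DSMB may be incomplete for the last 30 days. How many events would be missed cannot be estimated from the documents, which give neither an expected SAE rate nor a likely frequency of spontaneous reports.

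**What to change.** 1. In section 12.5, define the end of involvement as the latest of the follow-up assessment, the final four-weekly call and any make-up PT visit.
2. In section 10.3 and Table 1, add one call to the participant or proxy at or shortly after day 30 from that date, using the RAE telephone screening form already named in section 12.4.1. State that this call does not restart the window. For everyone reached, the uncovered tail falls from 30 days to 0.
3. If no call is made, say in section 12.5 that the last 30 days rest on passive reporting, and tabulate events from that period separately from actively ascertained RAEs.

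The cost is about 30 short calls by existing staff with an existing form, plus a small amendment. Participants who ask not to be contacted (section 7.6) could not be called, and the tables should show how many closing calls were completed. The third option costs only the wording and one extra table row, but it discloses the gap without closing it.
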